6. STUDY DESIGN

This is a prospective, single arm, non-randomized, multi-center observational study to record objective data in patients undergoing upper extremity arteriovenous fistula construction with autologous tissue for the purpose of eventual hemodialysis access, in whom the EchoMark implantable marker is placed at the site of vascular anastomosis and the EchoSure module is used to collect ultrasonic data.

The expected duration of this study will be from May 2020 to December 2021. Patients will be identified and recruited by the surgeons participating in the study, who will be determined at a later date. Patients who have been scheduled for creation of an upper extremity autologous arteriovenous fistula creation surgery will be identified as appropriate for study recruitment. The study details will be explained to identified patients and the consent process will begin for willing patients. Participants in the study will have EchoMark devices implanted at the time of the surgery. Monitoring of fistulae will be performed in the postoperative period. Patients who wish to terminate their participation in the research will no longer receive EchoSure ultrasound examinations of their fistula and will revert to the standard monitoring practice of their surgeon.

Stage 1: Patients will be monitored using the EchoSure ultrasound to collect data. Data will be analyzed in an attempt to formulate normative ranges for relevant variables such that clear, objective metrics consistent with healthy versus pathologic fistula healing are established.

Stage 2: Patients will be monitored via EchoSure ultrasound in addition to the standard of care currently followed by the surgeon. Decisions will be made by the vascular surgeon, using a combination of clinical data and the EchoSure data to determine if and when interventions need to be made to prevent failure of fistula maturation. We will then calculate the effect of the EchoMark and EchoSure on the rate of successful fistula maturation.

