With the implantation of any foreign material such as a radiologic marker (EchoMark), there is some risk of infection, inflammation or extrusion. Given the biocompatibility data collected by the company and the extensive prior use of the material in medicine, the probability of such risk is extremely low and has already been evaluated by the FDA during the approval process for EchoMark. There is risk that the ultrasound scan may create mild discomfort for the patient on the wound site. The likelihood and severity of this risk is low. If the patient begins to exhibit signs of infection, inflammation or extrusion, a clinical decision will be made by the team if the risk from the implantable device requires removal of the device. In these cases, the implantable device will be removed, and the patient will be monitored with conventional methods.

If ultrasound scanning is found to create discomfort to patient that exceeds that of traditional monitoring devices such as standard ultrasonography, the patient will be offered the option of discontinuation of EchoSure ultrasound scans and be monitored subsequently with conventional methods.

Despite the significant benefit of fistula surgery, there remains a significant risk of postoperative thrombosis, inappropriate fistula maturation, and continued reliance on prosthetic central vascular access for hemodialysis, all of which can cause serious morbidity and even mortality. By using this technology, it is possible that impending failure of fistula maturation can be detected early enough to salvage the fistula and prevent the impending fistula failure and associated morbidity.

Should the patient opt out of the study, they will be monitored with the current standard of care within the vascular surgeon's practice. This includes clinical observation and color Doppler ultrasonography per the surgeon's standard practice.

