Written informed consent, in accordance with applicable international standards and trial center regulations, shall be obtained from each subject, prior to the trial procedures. The investigator retains a copy of the signed informed consent document in each subject's record, and provides a copy to the subject.

The Investigator must obtain the written informed consent of all subjects, and must not allow any subject to participate in the investigation prior to obtaining governing institutional review board (IRB), research ethics board (REB) approval, or Ethics Committee (EC) approval. Before starting the trial, the investigator provides the trial Sponsor with a copy of the sample Informed Consent document approved by the IRB, REB, or EC with documented evidence that the IRB, REB, or EC approved the protocol and the informed consent.

Process of Consent

Patients eligible for the study will receive detailed written information on the trial, after which they will be asked to give *written* informed consent in accordance with the local clinical site's Ethics Committee. **Oral consent is not an acceptable substitute.**

Consent may only be obtained in person by a member of the study team delegated with consenting responsibilities. Consent will be obtained by a member of the research team in the patient's preoperative visit to clinic or in the pre-operative area prior to the initiation of anesthesia. The research team will take as much time as necessary to confirm full understanding of the study in the consent discussion. There will be sufficient time for the patient to consider the

study obligations and decide whether or not to participate, as study participation will not change clinical care and their data can be removed at any time if they choose to disenroll. Participation is fully optional.

Study personnel should explain that even if a patient agrees to participate in the study and signs the ICF, the patient may not be eligible to participate if he/she fails additional eligibility criteria or the surgical plans changes during the procedure.

Once signed, a copy of the Patient Informed Consent document and the Patient Information Sheet will be given to the patient.

A Screening and Enrollment Log will be maintained in the on-site clinical records located at the study site to document select information about candidates who are enrolled in the study as well as those who fail to meet the entry criteria.

Vulnerable Subjects

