10. STUDY PROCEDURES AND METHODS

Patients undergoing fistula creation procedures will be identified. The study will be explained to these patients and informed consent for participation in the study will be obtained from willing patients. A small, FDA-approved tissue marker will be implanted prior to closure of wounds following the Instructions for Use on the FDA-approved labelling.

Stage 1: The fistula will be assessed with intermittent EchoSure examinations, sometimes during routine dialysis visits (maximum 3x/week) to minimize travel. This will conclude when the fistula has entirely matured and the patient begins hemodialysis via the fistula or when the vascular surgeon declares that the fistula has failed despite any and all salvage attempts.

Stage 2: Similar to stage 1 but with implementation of the normative values for relevant variables that resulted from the data collected in stage 1, with subsequent use of the EchoSure flow information in the vascular surgeon's decision making. This stage will also conclude when a year has passed and the fistula is functioning or when the vascular surgeon declares that the fistula has failed despite any and all salvage attempts or that monitoring is no longer clinically necessary.

Actions to Be Taken by Site Staff	Screening and pre-operative evaluation	Clinic Visits	Initiation of dialysis or fistula failure
Consenting	X		
Initial Enrollment Form		X	
Nurse Scan Form		X	
EchoSure Scan		X	
Standard Clinical Exam		X	
End of Trial Period Form			X

11: DATA COLLECTION, ANALYSIS, AND MONITORING

Adverse events are not expected in this study. Unanticipated problems will be reported and discussed with the principal investigator and research coordinator. Patients will be regularly monitored for signs of infection, inflammation or device extrusion. Should the implantable device require removal, it will be removed, and patient will be monitored with conventional methods. The research team will periodically review its protocols to ensure maximal patient safety and data validity.

Source Documentation

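### The consent section says participation does not alter clinical care, which conflicts with the use of EchoSure data in Stage 2 intervention decisions

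*Combined protocol and SAP*

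**What the plan says.** All references are to the combined protocol and SAP.

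- **Section 9, Process of Consent.** Consent is written and taken in person, either at the pre-operative clinic visit or in the pre-operative area before anaesthesia. The time to decide is called sufficient on the ground that "study participation will not change clinical care", and that a patient who leaves can have the data taken out. No stage is named.
- **Section 6, Stage 2.** "Patients will be monitored via EchoSure ultrasound in addition to the standard of care currently followed by the surgeon". The surgeon then decides "using a combination of clinical data and the EchoSure data to determine if and when interventions need to be made".
- **Section 10, Stage 2.** The normative values obtained in Stage 1 are put into practice, "with subsequent use of the EchoSure flow information in the vascular" surgeon's decisions.
- **Section 8.** Stage 2 is described as the intervention cohort. A chi-square test between the Stage 1 and Stage 2 cohorts is to measure the benefit of intervening on early EchoSure findings.
- **Sections 6 and 7, leaving the study.** A patient who leaves has no further EchoSure scans and, in the words of Section 6, "will revert to the standard monitoring practice of their surgeon".
- **Section 6, risks.** With the implanted marker "there is some risk of infection, inflammation or extrusion". The protocol rates the probability as extremely low.
- **Section 12.** A near-duplicate of the consent paragraph appears here without the clause about clinical care.
- **Section 14.1.** The consent document is a separate attachment.

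**The concern.** The clause is more than a passing remark: it is one of the reasons given for regarding the consent time as adequate, including when consent is taken shortly before surgery. If it is untrue for Stage 2, that part of the rationale fails for Stage 2.

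The possible consequence for patients is conditional. If staff or the consent form repeat the clause, a Stage 2 patient could agree without understanding that study readings may contribute to a decision for a further or earlier procedure. If the form describes Stage 2 correctly, the fault stays within the protocol. Even then, an ethics committee and site staff would be working from two incompatible descriptions of the same stage.

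**Working it through.** No disputed figure is involved, so the check is a comparison of the text, stage by stage.

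**1. Scope of the clause.** Section 9 describes one consent process for the whole study. Neither the sentence nor its surroundings restricts it to Stage 1, so as written it covers Stage 2.

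**2. Set against each stage.**

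| Element | Stage 1 | Stage 2 |
|---|---|---|
| EchoMark implanted at surgery (Section 6) | Yes | Yes |
| EchoSure scans (Sections 6, 10) | Yes, for data collection and normative ranges | Yes, on top of the surgeon's standard care |
| EchoSure data used to decide on interventions (Sections 6, 10) | Not described | Yes, together with clinical data |
| Criteria derived within the study applied to care (Section 10) | No; they are being derived | Yes |
| EchoSure scans stop on leaving (Sections 6, 7) | Yes | Yes |

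**3. Reading the table.** For Stage 1 the clause is close to accurate as regards intervention decisions, since only data collection is described. For Stage 2 the third and fourth rows contradict it directly. The last row is a further sign, in both stages, that participation affects monitoring: if the scans were wholly independent of enrolment, withdrawal need not end them.

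**4. The analysis section agrees with the Stage 2 description.** Section 8 sets a standard-of-care success rate of 50% against 78% taken from a programme of ultrasound with early intervention. The plan's sample size reproduces from these inputs, reading its stated beta of 0.8 as power. With a two-sided alpha of 0.05 and no continuity correction:

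n = [1.960 × √(2 × 0.64 × 0.36) + 0.842 × √(0.50 × 0.50 + 0.78 × 0.22)]² / (0.78 − 0.50)² ≈ 45 per cohort

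Here 0.64 is the mean of 0.50 and 0.78. Power at 45 per cohort is 80.1%, and 45 / (1 − 0.25) = 60. These figures are not in question. They are relevant only because the 78% comes from a setting where ultrasound prompted early intervention, which is how Sections 6 and 10 describe Stage 2 and not how Section 9 does.

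**5. Extent.** Stage 2 enrols up to 60 patients, and the clause as written applies to all of them.

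**The case against.** **The consent form has not been seen.** This is the strongest objection, and it stands as a limit on the point. A reader might infer that patients will be consented on a false statement. The documents do not support that. The clause is the protocol's own reasoning about time; it is not a script or consent-form text. Section 9 also promises detailed written information, a form approved by an ethics body, and as much time as is needed to confirm understanding. Nor can it be assumed that the marker risks go undisclosed: the protocol states them, and the form may too.

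**The marker and scans may already be the surgeon's plan.** Sections 3 and 7 admit only patients whose surgeon has selected EchoMark and EchoSure for monitoring. The study is labelled observational, and Section 5 has the devices used according to their instructions. On this reading the marker and scans are partly planned care, and the clause is partly defensible. This part of the objection stands, so the implant alone is not a clear contradiction. It does not reach the use of Stage 1-derived values in Stage 2 decisions, and it sits awkwardly with scans ending on withdrawal.

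**Stage 2 could still be tested if the clause were true.** A reader might infer that an unchanged course of care would leave Stage 2 unable to test its hypothesis. That does not follow. Section 8 compares Stage 1 with Stage 2, not participants with non-participants. If surgeons adopted EchoSure-guided care whether or not a patient enrolled, participation would change nothing, yet the two cohorts could still differ.

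**Conclusion.** The point holds as an internal inconsistency. The unqualified clause in Section 9 is wrong for Stage 2 when read against Sections 6, 8 and 10, and it supports a stated reason for the adequacy of consent time. The eligibility criterion softens the conflict without removing it. It should be corrected, because it concerns the premise on which consent is sought. Harm to patients is not shown and depends on a consent form that is outside the reviewed documents.

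The extent is Stage 2, up to 60 participants. A reader might take the difference between 50% and 78%, which is 28 percentage points, as the share of patients whose care or outcome would change. The documents do not support that use. The 78% is a planning value borrowed from another programme, and Section 8 gives 30% to 70% for the prior literature behind its 50%. The same subtraction would therefore give anything from 78 − 70 = 8 to 78 − 30 = 48 points. A contrast between sequential, non-randomised cohorts would not isolate the effect of changed management, and none of these numbers measures a defect in consent.

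The conclusion assumes that Section 9 applies to both stages, as it reads, and that Sections 6 and 10 describe what is intended in Stage 2.

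**What to change.** 1. Reconcile Section 9 with Sections 6, 8 and 10. Either remove the clause about clinical care, as the parallel paragraph in Section 12 already does, or limit it to any stage for which it is true.
2. State in the consent process that, in Stage 2, EchoSure readings may contribute to decisions on interventions.
3. Restate why the time to decide is adequate in Stage 2 without relying on the removed clause.
4. Check that the separate consent form agrees with the corrected text and covers the marker risks described in Section 6. Amend the form only if it does not.

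The cost is protocol wording, consent wording if needed, and an IRB submission. Sample size and analysis are unaffected, and no change to how surgeons manage patients is proposed.

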10. STUDY PROCEDURES AND METHODS

Patients undergoing fistula creation procedures will be identified. The study will be explained to these patients and informed consent for participation in the study will be obtained from willing patients. A small, FDA-approved tissue marker will be implanted prior to closure of wounds following the Instructions for Use on the FDA-approved labelling.

Stage 1: The fistula will be assessed with intermittent EchoSure examinations, sometimes during routine dialysis visits (maximum 3x/week) to minimize travel. This will conclude when the fistula has entirely matured and the patient begins hemodialysis via the fistula or when the vascular surgeon declares that the fistula has failed despite any and all salvage attempts.

Stage 2: Similar to stage 1 but with implementation of the normative values for relevant variables that resulted from the data collected in stage 1, with subsequent use of the EchoSure flow information in the vascular surgeon's decision making. This stage will also conclude when a year has passed and the fistula is functioning or when the vascular surgeon declares that the fistula has failed despite any and all salvage attempts or that monitoring is no longer clinically necessary.

Actions to Be Taken by Site Staff	Screening and pre-operative evaluation	Clinic Visits	Initiation of dialysis or fistula failure
Consenting	X		
Initial Enrollment Form		X	
Nurse Scan Form		X	
EchoSure Scan		X	
Standard Clinical Exam		X	
End of Trial Period Form			X

11: DATA COLLECTION, ANALYSIS, AND MONITORING

Adverse events are not expected in this study. Unanticipated problems will be reported and discussed with the principal investigator and research coordinator. Patients will be regularly monitored for signs of infection, inflammation or device extrusion. Should the implantable device require removal, it will be removed, and patient will be monitored with conventional methods. The research team will periodically review its protocols to ensure maximal patient safety and data validity.

Source Documentation

The Investigator must maintain complete source documents on all trial patients who are enrolled in the trial or who undergo screening. Source documents include patient medical records, hospital charts, clinic charts, Investigator's patient trial files, as well as the results of diagnostic tests (e.g., laboratory tests) kept in an individual patient binder and stored in a secured and locked location and must be made available to the sponsor or designated monitor during site visits.

The following minimum information should be recorded in the patient's medical records:

- The date the patient entered the trial and the patient number
- The trial protocol number and the name of the Sponsor
- The date that informed consent was obtained
- Evidence that the patient meets trial eligibility requirements (e.g., medical history, trial procedures and/or evaluations)
- The dates of all trial related patient visits
- Evidence that required procedures and/or evaluations were completed
- Documentation of specific device used, if any
- Occurrence and status of any Adverse Events
- The date the patient exited the trial, and a notation as to whether the patient completed the trial or was discontinued, including the reason for discontinuation

DATA QUALITY ASSURANCE

Case Report Forms specific to the trial will be used for the collection and recording of data at the Investigational site. Investigators are responsible for the timely completion and storage of these forms.

All CRFs will be collected by the Investigator and entered into a database. All case report forms received will be reviewed, tracked and filed. Prior to data entry, a pre-entry review will be conducted to ensure that mandatory fields have been completed. Incoming data will be reviewed to identify inconsistent or missing data. All hard copy forms and data files will be secured to ensure confidentiality.

Investigators are to maintain all source documents, including diagnostic test reports, laboratory results, completed case report forms, supporting medical records and informed consent. The source documents will be referenced during monitoring visits to verify the information documented on the case report forms.

Only clinicians involved in the study will have access to the data. All data will be collected electronically through the medical record system. Access to source documents will be per respective EHR guidelines on computers that are encrypted and password protected. HIPAA compliance guidelines will be used at all time. Human subjects will not be directly identifiable, but only identifiable in the study database through identifying information (Hospital, MRN). The study data will be saved on a HIPAA compliant secure cloud service.

PATIENT CONFIDENTIALITY

All information concerning patients or their participation in this trial will be considered confidential. Only authorized Sonavex personnel and designated consultants and regulatory agencies will have access to these confidential files. Enrolled patients will be assigned a unique identifier that will be used to maintain confidentiality of each patient's medical information. Patient names and other protected health information will not be captured on the case report forms.

12: ETHICS

IRB approval will be sought from CPHS (Committee For the Protection of Human Subjects) for this study.

An individual knowledgeable about the study, likely a listed member of the study personnel, will obtain consent in person from individuals involved in this study. Consent will likely be obtained in clinic or in the pre-operative area prior to the initiation of anesthesia. The team will take as much time as necessary to confirm full understanding of the study in the consent discussion. There will be sufficient time for the patient to consider the study obligations and decide whether or not to participate. Participation will be fully optional.

13: REFERENCES

14: ATTACHMENTS

1. Consent Document

14.1: CONSENT DOCUMENT

Attached as separate document

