5. STUDY OBJECTIVES

Purpose

Stage 1: The primary objective of Stage 1 of the study is to collect data to verify the technology's performance in fistula monitoring. In Stage 1, EchoMark is implanted and monitoring is completed post-operatively. EchoSure data is then captured in an effort to establish normal ranges of the relevant variables in the context of appropriately maturing fistulae and their physiology, which is currently unknown.

Stage 2: The purpose of Stage 2 of the study is to evaluate the performance of the EchoMark and EchoSure (both FDA approved devices) as an ultrasound-based method of monitoring maturation of fistulae. The implant and ultrasound will be used as per IFU. The primary purpose of the study is to collect data on patient outcomes and assess whether or not the information generated from use of

EchoMark and EchoSure can decrease the fistula maturation failure rate and improve the patency of fistulas after up to a year.

Performance Goals

Stage 1:

Primary Performance Endpoint:

- Data collection to verify accuracy
- Data collection to understand the natural history of flow physiology in AV fistulas and classify fistulas that will fail

Primary Safety Endpoint:

- Procedure freedom from Serious Adverse Events (SAEs) during the EchoMark implantation procedure and subsequent post-operative period

Stage 2:

Primary Performance Endpoint:

- Failed fistula maturation rate

Secondary Performance Endpoints:

- Cumulative fistula patency at the end of 1 year
- Volumetric flow data
- Vessel caliber
- Total cost of episode of care

Primary Safety Endpoint:

- Procedure freedom from Serious Adverse Events (SAEs) during the EchoMark implantation procedure and subsequent post-operative care.

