Patients are free to withdraw consent at any time. Patients who wish to terminate their participation in the research will no longer receive EchoSure ultrasound examinations of their fistula and their data will be removed from the study.

8: STATISTICAL ANALYSIS

Stage 1:

We will recruit 60 patients for participation in this study who are planning to undergo elective construction of upper extremity autogenous hemodialysis access. The minimum sample size of 45 was determined assuming a 50% successful fistula maturation rate (based on past studies) to yield sufficient power to detect a difference in maturation between this cohort and the intervention cohort in the next aim. It also accounts for the quantity of patient volumes needed to develop a [REDACTED] based on our experience with EchoSure. Lastly, this provides sufficient power to detect a difference in fistula maturation success based on the flow rate (logistic regression power estimation; $\alpha = 0.05$, $\beta = 0.8$, OR 2.5 [from $\text{Pr}(H_0) 0.45$ and $\text{Pr}(H_1) = 0.65$]. As a buffer, based on institutional experience with clinical research and subject attrition a drop-out rate of 25% has been added to yield a total of 60 patients.

Using the EchoSure-derived conduit diameter and volumetric flow as observed values and Duplex-derived conduit diameter and volumetric flow as accepted values, the accuracy of EchoSure will be calculated. Logistic regression will be used to assess the correlation between successful maturation and EchoSure-derived values for flow and conduit diameter at two weeks. Cut points will be evaluated to establish EchoSure criteria for [REDACTED] [REDACTED]. Pearson's correlation will be performed on both EchoSure-derived and Duplex-derived values of volumetric flow and conduit diameter to determine correlation between EchoSure findings at two weeks and both EchoSure and Duplex findings at six weeks.

Stage 2:

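### The withdrawal rule removes a withdrawing patient's data with no exception for safety events already seen, so the reported SAE result can omit observed events (a cheap improvement)

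*Combined protocol and SAP*

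**What the plan says.** All references are to the combined protocol and SAP.

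- **Safety endpoint (section 5, Performance Goals).** Stage 1: "Procedure freedom from Serious Adverse Events (SAEs) during the EchoMark implantation procedure and subsequent post-operative period". Stage 2: "Procedure freedom from Serious Adverse Events (SAEs) during the EchoMark implantation procedure and subsequent post-operative care". No other safety endpoint is listed. The readable part of section 8 contains no safety analysis; some of that section is redacted.
- **Marker risks (section 6).** The plan accepts that "there is some risk of infection, inflammation or extrusion". It rates the probability as extremely low and adds that the risk "has already been evaluated by the FDA during the approval process for EchoMark". If such signs appear, the team may remove the marker and follow the patient by conventional methods.
- **Surveillance (section 11).** "Patients will be regularly monitored for signs of infection, inflammation or device extrusion". Also: "Unanticipated problems will be reported and discussed with the principal investigator and research coordinator".
- **Source records (section 11, Source Documentation).** The medical record must hold "Occurrence and status of any Adverse Events", the exit date and the reason for any discontinuation. Investigators keep source documents and completed case report forms.
- **Withdrawal (section 7).** Patients who end participation have no further EchoSure scans and "their data will be removed from the study". The consent text in section 9 is softer: it says that removal is possible. Section 6 describes termination and opting out without mentioning removal of data.

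**The concern.** A safety rate should describe everyone who received the implant. The section 7 rule makes membership of the analysed group depend on something that happens after implantation, and a marker problem may influence it. A patient who has an SAE and then withdraws consent is not counted as an event, and is not counted as implanted either. The plan states no exception for safety data, so a team that follows it literally has to leave the event out.

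At stake is the only safety endpoint in each stage. A result of 100% SAE-free could be reported although the investigators had seen an SAE. The same applies to any tally of marker-site infection, inflammation, extrusion or removal that the sponsor later chooses to report.

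**Working it through.** **Inputs from the documents.** Each stage enrols up to 60 patients, from a minimum of 45 with a 25% drop-out allowance (section 8). The plan's figure reproduces: 45 / (1 − 0.25) = 60, so the allowance is 15 patients. The documents do not say how many of those 15 would be withdrawals of consent. They give no safety figure to reproduce, no expected event rate and no withdrawal rate by event status. The values below for these are assumptions.

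**Step 1: one patient.** Suppose 1 of 60 implanted patients has an event and then withdraws.

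- All implanted patients kept: 1/60 = 1.7%, exact 95% CI 0.04% to 8.9%. SAE-free: 59/60 = 98.3%.
- Rule applied: 0/59 = 0%, exact upper limit 1 − 0.025^(1/59) = 6.1%. SAE-free: 100%.

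**Step 2: expected reported rate.** Let p be the true rate, a the probability that an affected patient withdraws after the event, and u the probability that an unaffected patient withdraws. After removal,

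reported rate = p(1 − a) / [p(1 − a) + (1 − p)(1 − u)].

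| a (affected) | u (unaffected) | true 1% reported as | true 5% reported as |
|---|---|---|---|
| equal to u | any | 1% | 5% |
| 10% | 5% | 0.0090 / (0.0090 + 0.9405) = 0.95% | 0.0450 / (0.0450 + 0.9025) = 4.7% |
| 50% | 25% | 0.0050 / (0.0050 + 0.7425) = 0.7% | 0.0250 / (0.0250 + 0.7125) = 3.4% |

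For rare events the rate is multiplied by roughly (1 − a)/(1 − u). That is 0.90/0.95 = 0.95 in the mild case and 0.50/0.75 = 0.67 in the severe case. The ratio a/u is 2 in both, so the base level of withdrawal matters as much as the ratio.

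**Step 3: events lost per stage.** The expected number of affected patients in 60 is 60p: 0.6 at 1% and 3 at 5%. The expected number removed is 60pa. In the mild case that is 0.06 and 0.3; in the severe case, 0.3 and 1.5.

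**Step 4: no association.** If withdrawal is unrelated to events, only precision is lost. With zero events the exact 95% upper limit is 1 − 0.025^(1/n): 6.0% for 0/60. If the whole 25% allowance were withdrawals, 45 patients would remain and the limit would be 7.9%.

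**The case against.** Four points on the other side have force.

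1. **The events are not lost to the record.** Section 11 requires adverse events and reasons for discontinuation in the medical record, and retention of source documents. This stands. The event leaves the study's data and result but remains traceable. A reader might infer that the plan erases safety events altogether; the documents do not support that.
2. **Marker removal is not withdrawal.** Sections 6 and 11 send such patients to conventional monitoring and do not call this leaving the study. This stands too. A reader might infer that every marker removal deletes the patient's data; the rule reaches only those who withdraw consent.
3. **Nothing shows that affected patients withdraw more often.** This is correct, and it is why the result is a range that includes no bias. The severe case also sets withdrawal among unaffected patients at the level of the plan's whole drop-out allowance, which is pessimistic.
4. **The expected event rate is small.** Section 6 calls the risk extremely low and already evaluated. At an assumed 1%, fewer than one affected patient per 60 is expected. This limits the practical weight, but with so few events a single removal can change the headline from 98.3% to 100%.

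A further stronger reading is that the plan is deficient because non-serious marker-site events enter no endpoint. They do enter none. However, any adverse event is already to be charted, the stated risk is extremely low, none or one event per stage is likely unless the true rate is well above 1%, and what counts as an SAE is not defined in the supplied text. A planned tally of these events is therefore mainly a reporting preference.

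**Conclusion.** The concern holds for the withdrawal rule. Section 7, applied as written, can take an observed SAE or marker problem out of the safety result. Section 9 reinforces this by telling patients that removal is available.

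The expected bias runs from none (equal withdrawal), through about 5% of the true rate in relative terms (10% against 5%), to about a third (50% against 25%). It points towards too low a rate only if affected patients withdraw more often than others. All withdrawal and event rates here are assumed; the documents support no single value. The sample size is not in question. This is a low-cost improvement to a stated rule, not a defect that undermines the study.

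**What to change.** **Main change.**

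- Section 7: on withdrawal, stop collecting new data but keep data collected up to that point. At a minimum keep all safety events, together with the implantation and exit dates of every withdrawing patient, so that unaffected withdrawers stay in the denominator too.
- Section 8: report the SAE endpoint by stage in all implanted patients, with exact 95% intervals.
- Section 9: bring the consent wording into line, so that patients know before signing that safety data already collected will be kept.
- Section 10: complete the End of Trial Period Form at withdrawal as well. The schedule now ties it to initiation of dialysis or fistula failure.

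**Cost.** A few sentences, one extra trigger for an existing form, and IRB approval of the wording. No extra patients are needed. The real downside is that patients can no longer have safety data already collected removed. Anyone who consented under the present wording was promised otherwise, so the change is best made before enrolment.

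**Optional and minor.** Tabulate marker-site infection, inflammation, extrusion and marker removal by stage, with follow-up time shown. The stage proportions would not be directly comparable. By section 3, Stage 1 follow-up ends at 24 weeks or at maturation or failure, whichever is earlier, while the second Treatments entry there (read as Stage 2) runs up to 52 weeks. A common 24-week window would not cure this, because Stage 1 patients whose fistula matures early leave before then.
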